### 1.1 Study design

CMBG453C12201 is a Phase II open-label, single-arm, multi-center study of MBG453 in combination with azacitidine and venetoclax in adult subjects with AML not suitable for intensive chemotherapy. The study consists of 2 parts: Part 1 is a Safety Run-in (including two cohorts tested sequentially) to assess whether MBG453 is safe when given in combination with azacitidine and venetoclax; Part 2 is the expansion phase to assess the efficacy of MBG453 when given in combination with azacitidine and venetoclax. Approximately 6 subjects will be enrolled at the starting dose level, 400 mg Q4W. Provided the starting dose level is determined to be safe, approximately 12 subjects will be enrolled at the second dose level (800 mg Q4W). If no safety concerns are identified at either dose level in the Safety Run-in part, approximately additional 68 subjects treated with MBG453 at 800 mg Q4W will be enrolled in the Expansion part. A total of approximately 80 subjects treated with MBG453 at the 800mg Q4W dose level (including those in the safety run-in) is planned. The number of subjects included in each study part/cohort is presented in [Figure 1-1](#).

**Figure 1-1** Study Design

\* The safety run-in cohort MBG453 400mg Q4W requires 3 evaluable subjects (approximately 6 enrolled subjects) to have been observed for at least 2 cycles.

\*\* The safety run-in cohort MBG453 800mg Q4W requires at least 9 evaluable subjects (approximately 12 enrolled subjects) to have been observed for at least 2 cycles.

\*\*\* To achieve a total of 80 subjects at the 800mg Q4W dose level.

Study treatment consists of cycles of MBG453 (400 mg or 800 mg) administered on Day 8 of each cycle in combination with azacitidine administered intravenous or subcutaneous at 75 mg/m^2 daily during 7 days at the beginning of each cycle (between Day 1 to Day 9 with 3 different regimens possible), and venetoclax administered orally at 400 mg daily or below when administered concomitantly with CYP3A4 inhibitors or P-gp inhibitors (following ramp up starting on Day 1). The planned duration of a cycle is 28 days. Crossover between the different MBG453 doses (400 mg and 800 mg Q4W) is not permitted at any time during the study: subjects included in the first cohort of the safety run-in part will be treated with MBG453 at the 400 mg Q4W dose level during the whole study participation and subjects included in the second cohort of the safety run-in part and in the expansion phase will be treated with MBG453 at the 800 mg Q4W dose level during the whole study participation. Study treatment may continue until the subject experiences disease progression (as defined by ELN 2017 Döhner et al 2017) or unacceptable toxicity.

The first safety review meeting to assess whether MBG453 400 mg Q4W is not meeting overdose criteria (i.e. an excessive incidence of Dose Limiting Toxicities (DLT)) when added

in combination with azacitidine and venetoclax (first cohort of the safety run-in part) will take place after the first 6 subjects treated with MBG453 400 mg Q4W have completed 2 cycles of treatment. If no safety concerned are observed at this dose level, a second safety review meeting to assess whether MBG453 800 mg Q4W is not meeting overdose criteria when added in combination with azacitidine and venetoclax (second cohort of the safety run-in part) will take place after the first 12 subjects treated with MBG453 800 mg Q4W have completed 2 cycles of treatment. Details on the definition of dose limiting toxicities (DLT) are presented in [Table 2-2](#).

The efficacy of MBG453 when given in combination with azacitidine and venetoclax will be assessed after all subjects have completed 12 cycles of treatment (primary analysis). Subjects will be followed thereafter for at least 3 years after the last subject had been enrolled (or earlier if all subjects had discontinued or moved to a rollover protocol or other option of continued treatment with MBG453). Based on this data, the final CSR will be written (final analysis). However, the primary analysis will be skipped as Novartis decided to early terminate this study, and all the analyses (except some exploratory analyses) will be performed and reported in the final CSR.

No randomization and no interim analysis are planned for this Phase II study.

[figure not shown]
## 1.2 Study objectives and endpoints

[Table 1-1](#) (which is a copy of the Table 2-1 from the study protocol) outlines the primary, secondary and [REDACTED] objectives and belonging endpoints. Further details are given in the statistical methods section of this SAP.

**Table 1-1 Objectives and related endpoints**

Objective(s)	Endpoint(s)
Primary objective(s)	Endpoint(s) for primary objective(s)

Safety run in + Expansion: To assess the complete remission (CR) rate of MBG453, administered at 800 mg Q4W, in combination with azacitidine and venetoclax in subjects with AML not suitable for chemotherapy

Safety run-in: To determine whether MBG453 at the tested dose levels is not meeting overdose criteria when added to azacitidine + venetoclax in subjects with AML not suitable for chemotherapy.

	

Proportion of subjects achieving a complete remission (CR) as per investigator assessment (Cheson et al 2003, Döhner et al 2017) will be determined when all subjects have completed at least 12 cycles of treatment with MBG453 + azacitidine + venetoclax or discontinued earlier.

Incidence of dose limiting toxicities (DLT) between Cycle 1 Day 8 and end of cycle 2.

Secondary objective(s)	Endpoint(s) for secondary objective(s)

To assess the measurable residual disease (MRD) negativity rate

	

Proportion of subjects with MRD negativity (a MRD negative sample determined by Multiparameter Flow Cytometry (MFC)-MRD and a bone marrow remission) in the full population and/or any subgroup of interest (CR, CR/CRi, CR/CRh)

Objective(s)	Endpoint(s)

 
To assess the CR/CRi rate and the duration of CR/CRi
 
	
 
Proportion of subjects achieving a complete remission (CR) or complete remission with incomplete hematologic recovery (CRi), as per investigator assessment (Cheson et al 2003, Döhner et al 2017)
 
Time from the date of the first documented CR/CRi to the date of first documented relapse or progressive disease or death due to any cause, whichever occurs first, as per investigator assessment (Cheson et al 2003, Döhner et al 2017)
 

 
To assess the duration of complete remission (CR)
 
	
 
Time from the date of the first documented CR to the date of first documented relapse or progressive disease or death due to any cause, whichever occurs first, as per investigator assessment (Cheson et al 2003, Döhner et al 2017)
 


 
To assess the CR/CRh rate and the duration of CR/CRh
 
	
 
Proportion of subjects achieving a CR or complete remission with partial hematologic recovery (CRh), as per derivation (Döhner et al 2022)
 
Time from the date of the first CR/CRh to the date of first relapse or progressive disease or death due to any cause, whichever occurs first, as per derivation (Döhner et al 2022)
 

 
To assess the Event-free Survival (EFS)
 
	
 
The time from start of treatment until date of death due to any cause, or relapse from CR, or treatment failure defined as failure to reach CR by Cycle 8 Day 1, whichever occurs first, as per investigator assessment (Cheson et al 2003, Döhner et al 2017)
 

 
To assess Overall Survival (OS)
 
	
 
The time from start of treatment to death due to any cause
 

 
To determine safety and tolerability of MBG453 when administered in combination with azacitidine and venetoclax
 
	
 
Incidence and severity of AEs and SAEs, changes in laboratory values and vital signs, incidence of notable ECG abnormalities
 

 
Characterize the pharmacokinetics (PK) of MBG453 when administered in combination with azacitidine and venetoclax
 
	
 
Pharmacokinetic parameters (serum concentrations for MBG453 and plasma concentrations for venetoclax)
 

 
To evaluate immunogenicity of MBG453 when given in combination of azacitidine and venetoclax
 
	
 
Anti-drug Antibody (ADA) prevalence at baseline and ADA incidence on-treatment
 

 
To assess the effect of MBG453 in combination of venetoclax + azacitidine on transfusion independence
 
	
 
Number and percent of all subjects who achieve transfusion independence on treatment, and from baseline respectively.
 

## 2. Statistical methods

### 2.1 Data analysis general information

The final analysis, as well as the analyses that were used for the safety review meetings of the safety run-in part of the study will be performed by Novartis.

SAS or R will be used to perform all data analyses and to generate tables, figures and listings.

As Novartis decided to early terminate the study, the study data will be analyzed and reported based on all data up to final DBL in the final CSR.

#### **Data included in the analysis / data cut-off handling**

For each of the safety review meetings a data cut-off date was established after the targeted number of subjects had completed 2 cycles of treatment. All safety data (including duration of exposure to study treatment, dose interruptions/reductions, study treatment discontinuation, etc.), demographics, disease history (including cytogenetics, risk category, de novo vs secondary, etc.), hematology data, blast counts from bone marrow and PK data with an assessment date or event start date (e.g. laboratory assessment date or start date of an adverse event) prior to or on the cut-off date was included in the analysis. The list of analyses to be presented at the time of the safety review meetings are provided in [Section 2.10](#).

For the final CSR, all data collected prior to final DBL will be included in the analysis.

#### **General analysis conventions**

Qualitative data (e.g., gender, race) will be summarized by means of contingency tables; a missing category will be included as applicable. Percentages will be calculated using the number of subjects in the relevant population or subgroup as the denominator.

Quantitative data (e.g., age, body weight) will be summarized by appropriate descriptive statistics (e.g. mean, standard deviation, median, 25th and 75th percentiles, minimum, and maximum).

#### **General definitions**

*“Investigational drug”* refers to MBG453.

*“Study treatment”* will refer to the combination of MBG453 with azacitidine and venetoclax.

*“Study treatment component”* refers to MBG453, azacitidine or venetoclax

Other general definitions are detailed in [Appendix Section 5.1](#).

### 2.2 Analysis sets

For the safety review meetings, the analysis sets defined below were restricted to the population enrolled in the safety run-in part and subjects were analyzed according to the dose regimen they have been assigned to: MBG453 400 mg Q4W for the first cohort and MBG453 800 mg Q4W for the second cohort. At the time of the second Safety Review meeting to assess the overtoxicity risk for the second cohort (800 mg Q4W dose level), the available data from the first cohort (400 mg Q4W dose level) were also displayed.

For the final analysis, the analysis sets defined below will include subjects from both the safety run-in and the expansion parts. Subjects will be analyzed according to the dose regimen they have been assigned to (MBG453 400 mg Q4W or MBG453 800 mg Q4W columns) and overall (“All subjects” column), unless otherwise specified.

## **Full Analysis Set**

The Full Analysis Set (FAS) comprises all subjects who received at least one dose of any component of the study treatment (i.e. at least one dose of MBG453 or at least one dose of azacitidine or at least one dose of venetoclax).

## **Safety Set**

The Safety Set includes all subjects from the FAS.

## **Dose-Determining Set**

The Dose-Determining Set (DDS) includes all subjects from the FAS enrolled in the safety run-in part who met the minimum exposure criterion and had sufficient safety evaluations, or experienced a dose limiting toxicity (DLT) starting from Cycle 1 Day 8 to the end of Cycle 2. Details on the definition of dose limiting toxicities (DLT) are presented in [Table 2-2](#). A subject will be considered evaluable for DLT if:

- Subject has received 2 infusions of MBG453 at the assigned dose level in Q4W dosing regimen, and has taken at least 75 % of the planned dose of azacitidine and venetoclax (i.e. for 2 cycles: 11 doses of azacitidine out of the 14 doses planned and 42 doses of venetoclax out of the 56 doses planned with a successful ramp up to full dose where full dose is equal to 400 mg or less when administered concomitantly with CYP3A4 inhibitors or P-gp inhibitors), and subject has had safety assessments for a minimum period of 2 cycles (from Cycle 1 Day 1 to the end of Cycle 2), or
- Subject has experienced a DLT within the DLT observation period from first dose of MBG453 to the end of Cycle 2. Note that subjects who experience toxicity that meets the criteria for DLT but occurs prior to the first dose of MBG453 will be considered not evaluable.

Note: A subject who leaves the study before receiving any dose of MBG453 will not be included in the DDS.

Note: For a subject with a grade 4 neutropenia, thrombocytopenia and pancytopenia (hematological toxicity that could be qualified as a DLT) occurred during the DLT evaluation period (from Cycle 1 Day 8 to the end of Cycle 2), a sufficient follow-up time will be considered to determine if the adverse event has to be qualified as a DLT. As per protocol, only persistent grade 4 neutropenia, thrombocytopenia and pancytopenia beyond Day 42 from the start of a study treatment cycle and is not related to leukemic infiltration will be considered to be a DLT (bone marrow evaluation may be required to determine if marrow aplasia is due to leukemia). Thus, in such a situation, the cut-off date for the safety review meeting could be delayed to enable to qualify or not this hematological toxicity as a DLT.

Note: The period from Cycle 1 Day 8 to the day before Cycle 3 Day 1 corresponds to the period from the first dose of MBG453 in Cycle 1 to the day before the first dose of azacitidine in Cycle 3. In case of Cycle 3 is not initiated, the period to consider for the DLT evaluation will be the period from the first dose of MBG453 in Cycle 1 to the maximum date between the last day of study treatment administration (azacitidine or venetoclax) in Cycle 2 and the theoretical last day of Cycle 2 (Cycle 2 Day 28).

### **Pharmacokinetic Analysis Sets**

The MBG453 and venetoclax pharmacokinetic analysis sets include all subjects from the Safety Set who provide at least one evaluable MBG453 PK concentration or one evaluable venetoclax PK concentration respectively for the two populations.

For a concentration to be evaluable:

- Dosing information must be properly documented (data and time of administration)
- For post-dose samples: planned dose of MBG453 or venetoclax respectively must be taken prior to sampling
- For pre-dose samples: the sample is collected before the next dose administration

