Additionally, the guidance indicated in [Table 6-5](#) below, provides instructions for infusion reaction, immune-related adverse events not covered by ASCO guidelines and a general guideline for non-hematologic non-immune-related toxicities that are clinically significant per investigator judgement and possibly attributable to the investigational drug. This general guideline will not apply in case of non-hematologic non-immune-related toxicities that are attributable to azacitidine, venetoclax and AML and its complications.

Deviations to dose interruptions, reductions and/or permanent discontinuations outlined in [Table 6-5](#) are not allowed.

Administration of MBG453 may be delayed due to toxicities. A scheduled dose may be delayed within a cycle by up to 14 days. If a dose cannot be administered within the planned window within the cycle, then the dose should be skipped. Next scheduled dosing may resume once the adverse event has resolved to \leq Grade 1 or baseline per the next planned treatment cycle. Dose reductions for MBG453 are not allowed.

Overall, for adverse events of potential immune-related etiology (irAE) that do not recover to \leq Grade 1 or baseline at a dose of immunosuppression of \leq 10 mg/day prednisone or equivalent (or as indicated in [Table 6-5](#)) within 12 weeks after initiation of immunosuppressive therapy, MBG453 must be permanently discontinued.

Table 6-5 Criteria for dose interruption and re-initiation of study drug MBG453 for adverse drug reactions

Worst Toxicity Grade (CTCAE v5.0)	Recommended Dose Modifications
Infusion Reaction	
Grade 1	Decrease infusion rate until recovery
Grade 2	
Stop infusion
 
Before restarting - pre-medicate according to local institutional guidelines.
 
Restart infusion at 50% of previous rate under continuous observation. Ensure that there is a minimum observation period of 1 hour prior to restarting the infusion(s). If the AE recurs at the reinitiated slow rate of infusion, and despite oral pre-medication*, then discontinue MBG453

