8.5.2.1 Pharmacokinetic and Immunogenicity blood collection and handling

The MBG453 PK, [REDACTED] and IG blood sampling schedule is outlined in [Table 8-9](#). A single blood sample of approximately 5 mL will be collected at each time point.

The venetoclax PK blood sampling schedule is outlined in [Table 8-10](#). A single blood sample of approximately 3 mL will be collected at each time point.

Blood samples will be taken by either direct venipuncture or an indwelling cannula inserted in a forearm vein opposite to the arm used for infusion. When PK is collected at the same time point as ECG, the PK sample should be taken immediately after ECG.

The exact date and clock times of drug administration and blood draws for PK, IG [REDACTED] assessment will be recorded on the appropriate eCRF.

After permanent discontinuation of MBG453, the samples scheduled for pre-MBG453 infusion and end of MBG453 infusion (within 2 hours) should no longer be collected.

Detailed instructions for the collection procedures, handling, and shipment of MBG453 PK, IG [REDACTED] samples, and venetoclax PK samples will be provided in the [CMBG453C12201 Laboratory Manual].

Table 8-9 MBG453 PK, IG [REDACTED] blood collection log

Cycle	Day	Scheduled Time Point*	PK sample (MBG453)	IG sample
1	1	Pre-azacitidine dose		
	8	Pre-MBG453 infusion	X	X
		End of MBG453 infusion (within 2 hours)	X	
2	8	Pre-MBG453 infusion	X	X
3	8	Pre-MBG453 infusion	X	X
		End of MBG453 infusion (within 2 hours)	X	
6	8	Pre-MBG453 infusion	X	X
9	8	Pre-MBG453 infusion	X	X
12	8	Pre-MBG453 infusion	X	X
18	8	Pre-MBG453 infusion	X	X
24	8	Pre-MBG453 infusion	X	X
EOT ¹		Anytime	X	X
30-Day Safety Follow-up		Anytime	X	X
150-Day Safety Follow-up ²		Anytime	X	X

Cycle	Day	Scheduled Time Point*	PK sample (MBG453)	IG sample	
Unscheduled ³	Anytime		X	X	

**All pre-dose samples must be collected within 2 hours before start of infusion*

¹ If EOT is due to reasons other than disease progression, an unscheduled PK and IG sample should also be collected at the time of confirmed disease progression.

² Samples at the 150 day safety follow-up visit can be collected at the Investigator's discretion if the follow-up visits are conducted at the site.

³ Unscheduled PK and IG samples may be collected at any time if clinically indicated or at the Investigator's discretion

Table 8-10 Venetoclax PK blood collection log

Cycle	Day	Scheduled timepoint*	PK sample (venetoclax)
1	8	Pre-venetoclax dose	X
3	8	Pre-venetoclax dose	X

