6	8	Pre-venetoclax dose	X

**All pre-dose samples must be collected within 30 min before dose administration*

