12.5.3 Pharmacokinetics

The respective PAS for MBG453 and venetoclax will be used in all pharmacokinetic data analysis.

MBG453 and venetoclax drug concentrations

[figure not shown]
MBG453 and venetoclax concentration data will be listed by subject, and visit/sampling time point. Descriptive summary statistics for MBG453 and venetoclax concentrations will be provided by visit/sampling time point. Summary statistics will include mean (arithmetic and geometric), SD, CV (arithmetic and geometric), median, minimum, and maximum, as well as the frequency (n, %) of concentrations below the lower limit of quantification (LLOQ) and reported as zero. Values below the LLOQ will be treated as missing for the calculation of the geometric means and geometric CV%. PK parameters (the minimum observed plasma or serum drug concentration (Cmin or Ctrough) and the maximum (peak) observed plasma or serum drug concentration (Cmax)) will be estimated and reported. Missing values for any PK parameters or concentrations will not be imputed and will be treated as missing.

All concentration data for MBG453 and venetoclax vs. time profiles will be displayed graphically. The concentrations collected before dose administration on Day 8 of Cycle 3 and beyond are Ctrough for MBG453.

As the half life of venetoclax is approximately 26 hours, the sample collected at Cycle 1 Day 8 will be considered as the baseline venetoclax concentration at steady state before any dose administration of MBG453. The impact of MBG453 on the venetoclax concentrations may be assessed by comparing concentrations before and after MBG453.

Population pharmacokinetic analysis

If data permit, a mixed-effects model may be applied to the serum MBG453 concentration-time data from this study along with other studies to generate post-hoc estimates of pharmacokinetic parameters using appropriate software to characterize MBG453 exposure and to determine the effects of intrinsic (i.e. demographic factors) and extrinsic covariates (e.g. combination partners) on MBG453 exposure. If there is sufficient data for analysis, the details of the population pharmacokinetic analyses may be provided in a separate reporting and analysis plan, and the results may be reported in a separate population pharmacokinetic report.

Immunogenicity analysis

Immunogenicity will be characterized descriptively by tabulating ADA prevalence at baseline and ADA incidence on-treatment.

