### 2.8.1 MBG453 and venetoclax drug concentrations

Pharmacokinetic analyses will be summarized for the MBG453 or venetoclax pharmacokinetic analysis set. MBG453 and venetoclax concentration data will be listed by dose level, subject, and visit/sampling time point. Descriptive summary statistics for MBG453 and venetoclax concentrations will be provided by dose level, visit/sampling time point, excluding concentrations at EOT, 30-day follow-up, 150-day follow-up visit and unscheduled visit. Summary statistics will include mean (arithmetic and geometric), SD, CV (arithmetic and geometric), median, minimum, and maximum, as well as the frequency (n, %) of concentrations below the lower limit of quantification (LLOQ) and reported as zero. Values below the LLOQ will be treated as missing for the calculation of the geometric means and geometric CV%. MBG453 and venetoclax concentration data obtained from samples collected outside of PK sample collection window as defined per protocol will be flagged and excluded for the summary statistics.

All concentration data for MBG453 vs. time profiles with arithmetic mean (+/- SD) and geo-mean will be displayed graphically, excluding concentrations at EOT, 30-day follow-up, 150-day follow-up visit and unscheduled visit.

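### No PK rule checks the time since the previous dose, so by-visit concentration summaries pool pre-dose samples taken at very different intervals

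*SAP*

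**What the plan says.** **Evaluability.** SAP 2.2 (Pharmacokinetic Analysis Sets), repeated in protocol 12.1, asks that dosing be documented. A post-dose sample also needs the planned dose to have been taken first. A pre-dose sample has one further condition: "For pre-dose samples: the sample is collected before the next dose administration".

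**Window exclusion.** SAP 2.8.1 adds that concentrations from "samples collected outside of PK sample collection window as defined per protocol will be flagged and excluded for the summary statistics". The protocol windows are in the footnotes to Tables 8-9 and 8-10. For MBG453: "All pre-dose samples must be collected within 2 hours before start of infusion". For venetoclax: "All pre-dose samples must be collected within 30 min before dose administration".

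**Pooling.** SAP 2.8.1 states: "Descriptive summary statistics for MBG453 and venetoclax concentrations will be provided by dose level, visit/sampling time point". It also plans MBG453 concentration–time plots with means.

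**Intervals the protocol allows.** For MBG453, section 6.5.3 says: "A scheduled dose may be delayed within a cycle by up to 14 days". A dose that misses this window is skipped. Sections 6.1.5 and 6.5.3 let a cycle start slip by 42 days before discontinuation is called for, and longer if the investigator sees clinical benefit. Section 8 moves the Day 8 assessments along with a delayed infusion. SAP 2.6.1 remarks that delayed cycles are frequent, and SAP 2.4.1 tabulates cycle lengths up to 70 days and over.

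**Label.** Protocol 12.5.3 says: "The concentrations collected before dose administration on Day 8 of Cycle 3 and beyond are Ctrough for MBG453". SAP version 2.0 dropped the PK parameters and does not use that term in 2.8.1.

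**The concern.** Both timing rules look forward to the next dose. A pre-dose concentration is governed mainly by what lies behind it: whether the previous dose was given, and how long ago. A sample drawn in the 2 hours before a late infusion is correctly timed by the plan's rules and keeps its nominal visit label, yet it may sit 42, 56 or 70 days after the last infusion. It is then averaged with samples taken at 28 days.

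PK is a secondary objective. With PK parameters removed, concentrations by visit are its main planned output. Protocol 12.5.3 invites the reader to treat the values from Cycle 3 onward as troughs of a four-weekly regimen. If the interval varies with toxicity delays, differences between visits or dose levels may reflect who was delayed as well as exposure at 400 or 800 mg Q4W.

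**Working it through.** The plan states no figure for this point, so there is none to reproduce.

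**1. Days since the last MBG453 infusion at an in-window pre-dose sample**

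Inputs: 28-day cycle with infusion on Day 8; within-cycle delay of up to 14 days, or a skip; cycle-start delay of 42 days.

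- On schedule: 28.
- Within-cycle delay before this infusion: 28 + 14 = 42.
- Previous infusion delayed 14 days, this one on time: 28 − 14 = 14.
- One skipped infusion: 2 × 28 = 56.
- Cycle-start delay of 42 days: 28 + 42 = 70.
- Both delays: 28 + 42 + 14 = 84, and more if the clinical-benefit exception is used.

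Each meets the SAP 2.2 rule, and each meets the 2-hour window because sampling moves with the infusion.

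**2. Effect on a single MBG453 sample**

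The documents give no MBG453 half-life. I assume t = 14 to 28 days and mono-exponential decline, so that C(d)/C(28) = 2^(−(d − 28)/t).

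| Days since infusion | t = 14 | t = 28 |
|---|---|---|
| 14 | 2^1 = 2.00 | 2^0.5 = 1.41 |
| 42 | 2^−1 = 0.50 | 2^−0.5 = 0.71 |
| 56 | 2^−2 = 0.25 | 2^−1 = 0.50 |
| 70 | 2^−3 = 0.13 | 2^−1.5 = 0.35 |

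Protocol 4.2 reports faster elimination at low concentrations, which would push the long-interval ratios lower still.

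**3. Effect on a visit summary**

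This depends on the share of off-schedule samples, which the documents do not give. As an illustration, suppose a share of 20% at one visit. The geometric mean is multiplied by ratio^0.2.

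- 20% at 56 days: 0.25^0.2 = 0.76 (t = 14) or 0.50^0.2 = 0.87 (t = 28), a fall of 24% or 13%.
- 20% at 14 days: 2.00^0.2 = 1.15 or 1.41^0.2 = 1.07, a rise of 15% or 7%.

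The sign depends on the mix.

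**4. Venetoclax**

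Protocol 12.5.3 gives a half-life of about 26 hours. Under protocol 6.1.1, a dose missed by more than 8 hours is not taken. A sample drawn after one missed daily dose, about 48 hours after the last, reads 2^(−24/26) = 0.53 of a 24-hour sample. It meets the 30-minute window and is summarised with the others.

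**5. Interval between two compliant infusions**

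Protocol 8 allows ±3 days at each visit, so two on-schedule infusions can be 28 − 6 = 22 to 28 + 6 = 34 days apart. Over that range the ratio to a 28-day sample runs from 2^(6/14) = 1.35 to 2^(−6/14) = 0.74 (t = 14), or from 1.16 to 0.86 (t = 28).

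**The case against.** Several counter-arguments stand and limit the point.

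- **Bias low.** A reader might infer that the MBG453 means are biased low. The documents do not support this: a delayed dose followed by an on-time one gives a 14-day interval and a high reading, and the share of each interval is not given.
- **Lost data.** A reader might infer that slightly early samples are thrown away. They pass the evaluability rule, which tests order only. Under SAP 2.8.1 they leave the summary statistics but stay in the listings. Whether the 2-hour and 30-minute limits are too tight is a matter of preference.
- **A wrong trough estimate.** SAP version 2.0 estimates no PK parameters and does not call these values troughs. The tables describe observed concentrations and feed no test.
- **Other outputs.** Listings and concentration plots are planned. Protocol 12.5.3 allows an optional population PK analysis, which could use the recorded dose and sampling times.
- **Reach.** After Cycle 1, scheduled pre-infusion sampling is confined to Cycles 2, 3, 6, 9, 12, 18 and 24, so the interval just before those visits matters most. When no infusion is given, Day 8 assessments move to Day 22 and there is no infusion to anchor a window.
- **Stakes.** The endpoint is descriptive, in a programme that has been stopped.

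None of this supplies a check on time since the previous dose. The optional model does not repair the by-visit tables, which are the output the SAP commits to.

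**Conclusion.** The gap is real and follows from the text alone. Neither the evaluability rule nor the window exclusion looks at the previous dose, so the by-visit summaries pool MBG453 samples taken from about 14 to 70 or more days after the last infusion. They also pool venetoclax samples taken after a missed dose with 24-hour samples. Because the intervals are linked to toxicity delays, the summaries cannot be read as Q4W pre-dose exposure.

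The single-sample ratios for MBG453 rest on an assumed half-life of 14–28 days and simple exponential decline. The venetoclax figure of 53% uses the protocol's own half-life and the same decline. No direction or size can be claimed for the visit means. The effect is confined to a descriptive secondary endpoint; the CR analysis is untouched.

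**What to change.** In SAP 2.8.1:

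- Derive the actual time since last dose for every pre-dose sample.
- For post-Cycle 1 MBG453 by-visit summaries and mean profiles, include a pre-dose sample only if the previous scheduled infusion was given and the interval lies in a pre-specified window around 28 days. A window of 22–34 days accommodates two ±3-day visits; a flat 28 ± 3 days would drop compliant samples.
- Exempt the Cycle 1 Day 8 pre-infusion MBG453 sample, which is a baseline with no previous infusion.
- For venetoclax, require that the previous day's dose was taken at the dose then prescribed for that subject, so that inhibitor-adjusted and reduced doses count.
- List the remaining samples, plot them against actual time since last dose, and show the all-samples summary alongside as supportive.

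Cost: SAP wording and one derived variable, from dose and sampling times that protocol 8.5.2.1 already requires to be recorded. The late-cycle summaries will hold fewer subjects, and the restricted summary describes subjects who stayed on schedule, which is why the all-samples version should sit beside it. Relaxing the 2-hour and 30-minute windows is optional and not part of this correction.
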